#### 4.3.2 Medical and surgical history

Medical history will be listed and summarized.

Pathologies associated with past medical and surgical history will be classified into primary system organ classes and preferred terms using MedDRA (version 21.1 or higher) and will be summarized by treatment group and overall using counts and percentages.

#### 4.3.3 Physical and neurological examinations

Physical and neurological examination abnormalities will only be listed. The listing for physical and neurological examinations will contain subject number, visit, examination date and time, body system and abnormalities.

#### 4.3.4 Treatment tolerability and compliance

The overall treatment tolerability of UB-312 in each study part is defined as the percentage of number of administered UB-312 doses divided by number of administered UB-312 doses plus number of missed UB-312 doses of participant(s) who dropped out due to drug-related AE(s).

All administrations (date/time) will be listed by presenting subject number, visit, dose, volume of dose, injection completion.

### 4.4 Safety and tolerability endpoints

The safety set is used to perform all safety analyses.

Baseline is defined as the last value prior to first dosing. Change from baseline will be calculated for all continuous safety parameters.

#### 4.4.1 Adverse events

The AE coding dictionary for this study will be Medical Dictionary for Regulatory Activities (MedDRA). It will be used to summarize AEs by primary system organ class (SOC) and preferred term (PT).

The observation period will be divided into 2 segments: pre-treatment and post-treatment.

- The pre-treatment period is defined as the time from the date of the informed consent to the time before the administration of first dose of study medication.

- The post-treatment period is defined as the time from after the first dose of study medication to the end of the study.

Pre-treatment AEs are defined as AEs that develop or worsen or become serious during the pre-treatment period.

Treatment-emergent AEs (TEAEs) are defined as AEs that develop or worsen (according to the investigator's judgement) or become serious during the post-treatment period.

The primary focus of adverse event reporting in the CSR will be TEAEs. Pre-treatment AEs will be described separately.

All AEs and SAEs will be displayed in listings. The listing will contain subject number, treatment, occasion, dosing date, SOC, PT, start date and time of AE, duration of AE, severity, SAE, relationship and chronicity.

Summaries of all TEAEs in each treatment group and overall (pooled Placebo versus pooled treatment groups), will include:

- The overview of AEs, summarizing number (%) of subjects with any TEAE/serious TEAE.
- The number and percentage of subjects with at least one TEAE by System-organ Class and Preferred Term.
- Summary of TEAEs by intensity (mild, moderate, severe, life-threatening, death), presented by System-organ Class and Preferred Term.
- Summary of TEAEs by causal relationship to the study drug, by System-organ Class and Preferred Term.

#### **4.4.2 Previous and Concomitant Medications/Therapy**

Previous and concomitant medications will be coded according to the World Health Organization (WHO) drug code and the anatomical therapeutic chemical (ATC) class code.

Medications will be classified into the following two groups:

- Previous medications are those that the participant took within the 30 days prior to the screening visit and prior to the first administration of the study drug at Week 1 (V1/baseline).
- Concomitant medications are those that the participant continued or started on or after the first injection of the study drug up to the end of the study.

These medications will be classified into anatomic and therapeutic classes using the World Health Organization (WHO) Drug Dictionary. Participants will only be counted once within each anatomic and therapeutic class.

Descriptive statistics including number of participants and percentage will be provided. No statistical testing for between-group difference will be performed.

All concomitant medications will be displayed in a listing. The listing will contain subject number, treatment, occasion, dosing date, start date and time of concomitant medication intake, duration, medication name, dose, regimen, route, and indication.

#### **4.4.3 Physical and neurological examinations**

Physical and neurological examination abnormalities (changes in specific findings compared to baseline) will only be listed. The listing for physical and neurological examinations will contain subject number, visit, examination date and time and abnormalities.

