Outcome Measures	
Primary Outcome Measures
 
Safety and tolerability will be assessed by adverse events (AEs), clinical laboratory assessments, vital signs, neurological and physical examinations, electrocardiograms (ECG), and safety MRI if applicable.
 
Immunogenicity will be measured by change from baseline of blood and CSF anti-aSyn antibody titers.
 
Exploratory Outcome Measures
 
Exploratory outcome measures may include but are not limited to the following:
 
 • Antibodies against different molecular forms of aSyn such as monomers, oligomers and fibrils • Antibodies against components of the vaccine, such as CpG1 and UBITh1 • Total and free aSyn concentrations in blood and CSF • T-cell ELISpot specific for the immunizing peptide (UB-312), the carrier (UBITh1), and the target (aSyn epitope) • For Part B only, exploratory clinical efficacy and safety assessments based on the Movement Disorder Society – Unified Parkinson's Disease Rating Scale (MDS-UPDRS, Parts II and III) and Montreal Cognitive Assessment (MoCA) • For Part B only - Biomarker-based target engagement will be measured by detecting misfolded aSyn in pre- and post-immunization CSF samples of PD patients using the protein misfolding cyclic amplification (PMCA) assay
Phase	1
Study Population	Eligible males and females, aged 40 to 85 years, inclusive at screening. For Part B only, participants with a diagnosis of Parkinson's Disease confirmed by a neurologist, and who present in Hoehn & Yahr Stages ≤ III.
Total Expected Number of Participants	Approximately 50 healthy participants (8 participants in the lowest dose cohort and 7 participants per cohort for ascending cohorts) and approximately 20 participants with clinically established PD will be enrolled to receive UB-312 treatment or matching placebo.

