7. MRI will be performed between Screening and baseline (V1). For participants who were screen failed and subsequently re-screened to accommodate deployment of the COVID-19 booster vaccination, the original MRI performed during the initial screening can be accepted provided it was performed within 90 days of the start of treatment (Day 1).
8. For females of childbearing potential only, blood pregnancy test at screening and urine test at other visits. For part B, a urine pregnancy test will also be performed prior to DaTscan (in addition to the blood pregnancy test).
9. Specific measurements are listed in Section 10.6 of the protocol. Hematology and chemistry results will be available prior to the first study drug administration.
10. Inflammatory measures in blood will include: C-reactive protein (CRP), erythrocyte sedimentation rate (ESR). At Screening only: antinuclear antibody (ANA), IgM rheumatoid factor (RF) and anti-cyclic citrullinated peptide (anti-CCP). CRP level results will be available prior to study drug administration at each applicable visit. For participants who have undergone COVID-19 booster vaccination, inflammatory markers at Screening may be repeated if results at Screening are not within acceptable limits as required by the protocol.
11. Additional blood samples will be collected for future medical research in participants who consent.
12. Hoehn & Yahr for Screening only.
13. Historic DaTscan is acceptable.
14. Participants will stay for 6 hours after injection for safety observation. Participants will have a 24-hour telephone call. Daily injection site review and temperature recording will be done at home by the participant for 6 days, starting from the day after study drug administration.
15. Individual tests will be performed at Investigator's discretion.
16. Antibody measures in blood, including but not limited to: anti-aSyn target epitope (monomers, oligomers and fibrils may be analysed), anti-UBITh, anti-CpG1.
17. Full physical examination at screening and last FU visit, brief physical examination during the other visits.
18. Performed at the last follow-up visit only.
19. Only performed if PBMC sample for ELISpot not collected at V8.

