## 1.8 Planned changes to endpoints or analyses from the protocol

### 1.8.1 Planned changes to endpoints

Not applicable.

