## 2.2 Safety and tolerability endpoints

- Treatment emergent AEs
- Serious treatment emergent AEs
- Treatment emergent AEs leading to treatment discontinuation
- Concomitant medication
- Physical and neurological examinations
- Clinical laboratory tests
  - Haematology
    - Haemoglobin (unit: mmol/L)
    - Haematocrit (unit: L/L)
  - Chemistry
    - Sodium (unit: mmol/L)
    - Potassium (unit: mmol/L)

- Erythrocytes (unit: 10E12/L)
- Mean Cellular Volume (MCV; unit: fL)
- Mean Cellular Haemoglobin (MCH; unit: fmol)
- Mean Cellular Haemoglobin Concentration (MCHC; unit: mmol/L)
- Leucocytes (unit: 10E9/L)
- Platelet count (unit: 10E9/L)
- Eosinophils (unit: 10E9/L)
- Basophils (unit: 10E9/L)
- Neutrophils (unit: 10E9/L)
- Lymphocytes (unit: 10E9/L)
- Monocytes (unit: 10E9/L)
- Urea (unit: mmol/L)
- Uric Acid (unit: mmol/L)
- Creatinine (unit:  $\mu$ mol/L)
- Total Bilirubin (unit:  $\mu$ mol/L)
- Conjugated Bilirubin (unit:  $\mu$ mol/L)
- Albumin (unit: g/L)
- Total Protein (unit: g/L)
- Aspartate Amino Transaminase (ASAT; unit: U/L)
- Alanine Amino Transaminase (ALAT; unit: U/L)
- Glucose (unit: mmol/L)
- Urinalysis
  - Bilirubin (levels: Negative, +, ++ and +++)
  - Blood (levels: Negative; Non-haemolyzed 10 ery/ul; Non-haemolyzed 80 ery/ul; Haemolyzed 10 ery/ul; 25 ery/ul; 80 ery/ul; 200 ery/ul)
  - Glucose (levels: Negative; 5.5 mmol/l; 14 mmol/l; 28 mmol/l; 55 mmol/l;  $\geq$ 111 mmol/l)
  - Ketone (levels: Negative; 0.5 mmol/l; 1.5 mmol/l; 4 mmol/l; 8 mmol/l; 16 mmol/l)
  - Leucocytes (levels: Negative; 15 leuco/ul; 70 leuco/ul; 125 leuco/ul; 500 leuco/ul)
  - Nitrite (levels: Negative; Positive 1; Positive 2)
  - Protein (levels: Negative, trace, 0.30 g/l; 1 g/l; 3 g/l;  $\geq$  20 g/l)
  - Specific gravity (levels: 1.000, 1.005; 1.010; 1.015; 1.020; 1.025; 1.030)
  - Urobilinogen (levels: 3.2  $\mu$ mol/l; 16  $\mu$ mol/l; 33  $\mu$ mol/l; 66  $\mu$ mol/l; 131  $\mu$ mol/l)
  - pH (levels: 5.0; 6.0; 6.5; 7.0; 7.5; 8.0; 8.5)
- Vital signs
  - Temperature ( $^{\circ}$ C)
  - Pulse Rate supine (unit: bpm)
  - Systolic BP supine (unit: mmHg)
  - Diastolic BP supine (unit: mmHg)
  - Respiratory rate (unit: br/minute)
- 12-Lead electrocardiogram (ECG)
  - Diagnosis
  - Heart Rate (HR) (unit: bpm)
  - PR interval (unit: msec)
  - QRS duration (unit: msec)
  - QT interval (unit: msec)
  - QTcF (unit: msec)

- Local tolerability at injection site
  - Diarrhoea (levels: No; Yes, 1-3 times; Yes, 4-6 times; Yes, >6 times)

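### The neurological examination, a primary safety outcome, gets only a listing with no result by treatment group (SAP 4.4.3), and safety MRI is missing from the SAP's endpoints and analyses without being declared

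*SAP*

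**What the plan says.** The Protocol synopsis (Outcome Measures) defines the primary safety outcome through adverse events, laboratory tests and "vital signs, neurological and physical examinations, electrocardiograms (ECG), and safety MRI if applicable".

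SAP 2.2 carries "Physical and neurological examinations" into its list of safety endpoints. MRI is not in that list.

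For post-baseline data, SAP 4.4.3 says: "Physical and neurological examination abnormalities (changes in specific findings compared to baseline) will only be listed". It then fixes the columns: "The listing for physical and neurological examinations will contain subject number, visit, examination date and time and abnormalities". The baseline section, SAP 4.3.3, has the same rule ("Physical and neurological examination abnormalities will only be listed") and adds only a body-system column.

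In the supplied SAP text, MRI appears in the abbreviations, as a contraindication in the medical history items (2.1), and in the Appendix 1 schedule with its footnote 7. It is in none of the safety analyses under 4.4, nor among the Part A interim outputs (1.11.2). Under planned changes to endpoints, SAP 1.8.1 states "Not applicable".

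**The concern.** A component of the primary safety outcome should reach the report in a form that lets a reader set UB-312 against placebo. For the neurological examination the plan stops at a list of individual findings. It does not show which group each finding belongs to, how many participants had one, or how many were examined. The vaccine is meant to raise antibodies to alpha-synuclein in blood and CSF, and Part B enrols people with Parkinson's disease, so readers will want this comparison.

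For MRI the issue is narrower. A component named in the Protocol has no planned output, and the SAP section meant for recording such departures says there are none.

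**Working it through.** No figure in the plan is at issue, so the main check sets the primary safety components side by side with their planned display.

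| Component (Protocol synopsis) | SAP section | Planned display | By treatment group? |
|---|---|---|---|
| Adverse events | 4.4.1 | Listing with treatment column; tables | Yes |
| Vital signs | 4.4.4 | Descriptive summary | Yes |
| ECG | 4.4.5 | Descriptive summary | Yes |
| Haematology, chemistry, urinalysis | 4.4.6 | Summaries or frequency tables; shift tables | Yes |
| Neurological and physical examinations | 4.4.3 | Listing only: subject, visit, date/time, abnormality | No |
| Safety MRI, if applicable | none | none | No |

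Injection site reactions (4.4.7), diary symptoms (4.4.8) and inflammatory markers (4.4.9) are also summarised by treatment group. The concomitant medication listing (4.4.2) has a treatment column. Physical examination shares the gap, so it is not confined to the nervous system.

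**Can the examination be tabulated?** SAP 2.1 lists eleven neurological items. Ten have Yes/No levels, and one of these is an overall item for any significant abnormality. A participant-level count is therefore feasible. Item-level counts are less secure: SAP 2.1 and schedule footnote 5 make most post-dose examinations brief, and the supplied text does not say which items the brief version covers.

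**Can MRI be compared by arm?** In the SAP Appendix 1 schedule the MRI row is marked only before the first dose and at unscheduled visits. Footnote 15 leaves unscheduled tests to the investigator's discretion. There is no planned post-dose dataset, so a listing and counts are the most that can be asked for.

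**Denominators.** These come from the allocation table in SAP 1.10, which agrees with the Protocol synopsis. (A sentence in SAP 1.10 puts twelve participants in Cohort 8; the table and the synopsis give ten, which I use.)

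- Part A: active 7 × 6 = 42; placebo 2 + 6 × 1 = 8; total 50, as planned.
- Part B: active 2 × 7 = 14; placebo 2 × 3 = 6; total 20, as planned.
- Overall: 42 + 14 = 56 active and 8 + 6 = 14 placebo; total 70.

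**What a table could show.** If none of n participants has a finding, the one-sided 95% upper bound on the true rate is 1 − 0.05^(1/n).

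| n | Group | Upper bound |
|---|---|---|
| 6 | One Part A active cohort, or Part B pooled placebo | 39% |
| 7 | One Part B active cohort | 35% |
| 8 | Part A pooled placebo | 31% |
| 14 | All Part B active | 19% |
| 42 | All Part A active | 7% |

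A single cohort says little. Pooled active rows say more, and SAP 4.4.1 already pools in that way for adverse events.

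**The case against.** The best defence is that listing rare, mixed findings is reasonable in a small exploratory Phase 1 trial, and that nervous-system safety is covered elsewhere. Treatment-emergent adverse events are tabulated by treatment group, system organ class, intensity and causality (4.4.1). In Part B, MDS-UPDRS Parts II and III and MoCA are summarised by treatment (4.5 and 2.3), and the Protocol describes them as serving safety as well as efficacy. This stands in part: by-treatment information exists, but it is indirect. The supplied text has no rule that an examination finding must be recorded as an adverse event, an adverse event table does not give the number examined, and Part A has neither rating scale.

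A reader might infer more than the documents support in four ways.

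- **That the Part B listing would be filled with pre-existing Parkinson's signs.** The parenthesis in 4.4.3 limits the listing to changes from baseline, and baseline findings have their own listing in 4.3.3.
- **That the pre-dose MRI was scheduled as a comparator for later scans.** No passage gives its purpose. Exclusion criterion 1 names imaging among the eligibility results, which is an equally available reading.
- **That a by-arm MRI comparison has been dropped.** None was ever possible from the schedule.
- **That the data are lost.** Subject numbers identify the cohort (1.10), and the demographics listing pairs subject number with treatment (4.3.1), so the link can be rebuilt after unblinding. The display is simply not planned.

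Small cells are a fair limit on any table. They apply equally to the other safety tables, which the SAP nevertheless plans.

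**Conclusion.** The point holds in a limited form. SAP 4.4.3 leaves the neurological examination, a primary safety outcome, without a direct by-treatment result for any of the 70 planned participants. Safety MRI, primary only where applicable, is missing from SAP 2.2 and 4.4, and 1.8.1 does not declare this. The plan should be changed, but the gap is one of presentation: no data are lost, and it does not show that a nervous-system safety signal would go unseen.

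The conclusion assumes that the text not supplied adds nothing on either matter. Only the synopsis and schedule of the Protocol were available, and rules on recording findings as adverse events, or on when a safety MRI applies, could sit in its body. Some SAP pages were also removed, but its table of contents shows no MRI section.

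**What to change.** - **SAP 4.4.3, listing.** Add treatment group and examination item to the columns.
- **SAP 4.4.3, table.** Add one descriptive table by study part and treatment group, with placebo pooled within part. It should give the number and percentage of participants with any new or worsened post-dose neurological abnormality against the pre-dose examination, with the number examined as denominator. Show item-level counts only for items actually assessed at the brief examinations.
- **Definition.** Yes/No items show a new finding but not a worsening, which has to be read from the recorded description. Make that classification before unblinding.
- **Safety MRI.** Add it to SAP 2.2 and 4.4 as a listing with treatment, plus the number of participants scanned after dosing and the number with a finding per treatment group. Otherwise declare the omission in 1.8.1.

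The cost is SAP wording, one table, an extended listing and a short MRI listing with its counts, all from data the trial already collects. The drawback is small cells (6 or 7 active per cohort; pooled placebo 8 in Part A and 6 in Part B), so the table should be labelled descriptive. Nothing here changes the conduct of the trial or the care of participants.

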#### 4.4.4 Vital signs

At each time point, absolute values and change from baseline of vital signs will be summarized by treatment group using descriptive statistics of n, mean, SD, SEM, median, Min, and Max values.

The number of available observations and out-of-range values (absolute and in percentage) will be listed. Values outside the reference range will be flagged in the listing. 'H' and 'L', denoting values above or below the investigator reference range (when present), will flag as out-of-range results in the listing.

#### 4.4.5 12-lead ECG

At each time point, absolute values and change from baseline of ECG numeric variables will be summarized by treatment group and time with n, mean, SD, SEM, median, Min, and Max values.

The number of available observations and out-of-range values (absolute and in percentage) will be presented. Values outside the investigator's normal range will be flagged in the listing. 'H' and 'L', denoting values above or below the investigator reference range (when present), will flag out-of-range results.

#### 4.4.6 Clinical laboratory tests

All laboratory data (including re-check values if present) will be listed chronologically. 'H' and 'L', denoting values above or below the investigator reference range (when present), will flag out-of-range results. Shift tables will be included for haematology, chemistry and urinalysis.

##### 4.4.6.1 *Haematology and chemistry*

At each time point absolute values and change from baseline of the haematology and chemistry variables will be summarized by treatment group and time with n, mean, SD, SEM, median, Min, and Max values.

##### 4.4.6.2 *Urinalysis*

The categorical data of the urinalysis will be summarized by treatment group and time in frequency tables by variable.

##### 4.4.6.3 *Urine Drug screen*

Urine drug screen values will be listed.

##### 4.4.6.4 *Virology*

Virology results values will be listed.

#### 4.4.7 Local tolerability at the injection site (ISR)

The number and percentage of participants with reaction at injection site will be summarized and presented by treatment group and overall.

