Study Design	
This is a two-part randomized, double-blind, placebo-controlled study. Part A of the study with healthy participants will consist of dose escalation and cohort staggering for up to 7 planned dose levels or placebo. Part B of the study with PD participants will begin after interim analysis review of data collected during Part A, once all Part A participants complete assessments at Week 21 and the optimal dose(s) is selected based on safety, tolerability and immunogenicity of UB-312. All eligible participants will be enrolled in a 44-week study consisting of 20 weeks of treatment and 24 weeks of follow-up and undergo assessments as outlined in the Schedule of Assessments (Table 1).
 
Screening Phase (Part A and Part B):
 
After providing informed consent, participants will undergo screening assessments to determine eligibility to participate. All screening assessments are to be completed within 6 weeks prior to randomization at Visit 1.
 
Treatment Phase (Part A):
 
Eligible healthy participants will be enrolled into one of the 7 treatment cohorts. The first/lowest dose cohort (40 µg) will comprise 8 participants, randomized 6 active:2 placebo. The remaining cohorts will comprise 7 participants, randomized 6 active:1 placebo. The treatment arms are as follows:
 
• Participants assigned to Cohort 1 will receive 40 µg UB-312 or matching placebo (0.2 mL) at Week 1, Week 5 and Week 13.• Participants assigned to Cohort 2 will receive 100 µg UB-312 or matching placebo (0.5 mL) at Week 1, Week 5 and Week 13.• Participants assigned to Cohort 3 will receive 1 dose of 40 µg UB-312 or matching placebo (0.2 mL) at Week 1, followed by 300 µg UB-312 or matching placebo (0.3 mL) at Week 5 and Week 13.• Participants assigned to Cohort 4 will receive 300 µg UB-312 or matching placebo (0.3 mL) at Week 1, Week 5 and Week 13.• Participants assigned to Cohort 5 will receive 1 dose of 40 µg UB-312 or matching placebo (0.2 mL) at Week 1, followed by 1000 µg UB-312 or matching placebo (1 mL) at Week 5 and Week 13.• Participants assigned to Cohort 6 will receive 1000 µg UB-312 or matching placebo (1 mL) at Week 1, Week 5 and Week 13.• Participants assigned to Cohort 7 will receive 2000 µg UB-312 or matching placebo (2 mL) at Week 1, Week 5 and Week 13. 
Dosing of cohorts will be staggered for safety. The first 2 participants (1 active and 1 placebo) enrolled into Cohort 1 will be observed for 24 hours at the study site to ensure there are no serious acute reactions prior to dosing of the remaining participants within the cohort. Once all participants within a cohort have been observed for 1 week following their first dose of study medication, available safety data will be reviewed before progressing to the next higher dose cohort. Cohorts 3 and 4 will be randomized and dosed concurrently, as will Cohorts 5 and 6.
 
Participants in all cohorts will stay in the Clinical Research Unit approximately 6 hours after each dose, will have a phone call 24 hours after each dose and will have an onsite visit 1 week after each dose of study IP, to review for any injection site reactions and/or adverse events.

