1.1 Study Schematic

Figure 1 Study Design Schematic

[figure not shown]

Table 1 **Study Schedule of Assessments**

Visit	Screening	V1* Vaccination 1	V2	V3 Vaccination 2	V4	V5	V6 Vaccination 3	V7	V8	EOT or ET	Unscheduled Visit ¹⁵	Follow-Up
Week	Up to 6 weeks	1	2	5	6	9	13	14	17	21	N/A	29, 37, 45
Day*	-42 ~ 0	1¹⁴	8 (± 1)	29¹⁴ (± 3)	36 (± 3)	57 (± 3)	85¹⁴ (± 3)	92 (± 3)	113 (± 3)	141 (± 7)	N/A	197, 253, 309 (± 7)
Free and total aSyn ¹		X	X	X	X	X	X	X	X	X	X	X
ELISpot ¹		X							X	X ¹⁹		
HLA typing ¹		X										
Blood collection for future research ^{1,11}		X	X	X	X	X	X	X	X	X		
CSF collection ^{1,21}		X								X	X	X ¹⁸
Study Drug IM Injection		X		X			X					
Injection Site Reaction review ^{1,3}		X ¹⁴	X	X ¹⁴	X		X ¹⁴	X			X	
For Part B only												
Hoehn and Yahr	X											
MDS-UPDRS (Parts II to III ^{1,12})		X								X	X	X ¹⁸
DaTscan	X ^{8,13}											
MoCA		X								X		X ¹⁸

AE=adverse event; CSF=cerebrospinal fluid; ECG=electrocardiogram; EOT = End of Treatment; ET = Early Termination; HBV = Hepatitis B virus; HCV=hepatitis C virus; HIV = human immunodeficiency virus; IM=intra-muscular; MDS-UPDRS=Movement Disorders Society – Unified Parkinson’s Disease Rating Scale; MoCA = Montreal Cognitive Assessment; MRI=magnetic resonance imaging; SAE=serious adverse event

* Time points for all visits are relative to Day 1 (day of first IMP administration). Every effort should be made to schedule visits as close as possible to the time point specified in the Schedule of Assessments. If a visit cannot be scheduled within the specified window, the timing of the visit and procedures should be discussed with the Sponsor.

1. Prior to administration of study IP at each applicable visit. Screening and V1 visits can be rescheduled if measured for moderate or severe illness and/or fever $>38.0^{\circ}$ Celsius within 1 week prior to visit.
2. AEs/SAEs recorded from time of informed consent up to and including Follow-up.
3. Also performed 45 minutes (+/- 15 minutes) and approximately 6 hours after administration of study IP at each applicable visit.
4. Including height (screening only); no need to repeat weight measurement for post-injection vital signs.
5. Full neurological exam at screening and last FU visit, brief neurological examination at other visits.
6. ECG in triplicate.

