For Part B: dose(s) levels were selected based on interim analysis of safety, tolerability and immunogenicity data from all participants in Part A.

Cohort	Week 1	Week 5	Week 13
8	300 µg (0.3 mL), placebo	100 µg (0.5 mL), placebo	100 µg (0.5 mL), placebo
9	300 µg (0.3 mL), placebo	300 µg (0.3 mL), placebo	300 µg (0.3 mL), placebo

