  - Dizziness (levels: No; Mild: Does not interfere with daily life; Moderate: Interfere with daily life; Severe: Seriously hinder daily life)
  - Fatigue (levels: No; Mild: Does not interfere with daily life; Moderate: Interfere with daily life; Severe: Seriously hinder daily life)
  - Fever (levels: No, <38.0 °C; Yes, 38.0-38.4 °C; Yes, 38.5-38.9 °C; Yes, 39.0-40.0 °C; Yes, >40.0 °C)
  - Hard knot at injection site (levels: No; Yes, <2.5 cm in diameter; Yes, 2.5-5 cm in diameter; Yes, 5.1-10 cm in diameter; Yes, >10 cm in diameter)
  - Headache (levels: No; Mild: Does not interfere with daily life; Moderate: Interfere with daily life; Severe: Seriously hinder daily life)
  - Muscle pain (levels: No; Mild: Does not interfere with daily life; Moderate: Interfere with daily life; Severe: Seriously hinder daily life)
  - Nausea/Vomiting (levels: No; Yes, 1-2 times; Yes, 3-4 times; Yes, >4 times)
  - Other abnormalities at injection site (levels: No or Yes)
  - Painfulness at injection site (levels: No; Mild: Does not interfere with daily life; Moderate: Interfere with daily life; Severe: Seriously hinder daily life)
  - Physical discomfort (levels: No; Mild: Does not interfere with daily life; Moderate: Interfere with daily life; Severe: Seriously hinder daily life)
  - Redness at injection site (levels: No; Yes, <2.5 cm in diameter; Yes, 2.5-5 cm in diameter; Yes, 5.1-10 cm in diameter; Yes, >10 cm in diameter)
  - Swelling at injection site (levels: No; Yes, <2.5 cm in diameter; Yes, 2.5-5 cm in diameter; Yes, 5.1-10 cm in diameter; Yes, >10 cm in diameter)
  - Tenderness at injection site (levels: No; Mild: Slightly uncomfortable when pressure; Moderate: Discomfort upon movement; Severe: Discomfort at rest)
- Participant-reported local tolerability at injection site and systemic complaints (eDiary app)
  - Painfulness at injection site in past 24 hours (Dia\_Pain; levels: No; Mild: Does not interfere with daily life; Moderate: Interfere with daily life; Severe: Seriously hinder daily life)
  - Tenderness at injection site in past 24 hours (Dia\_Tender; levels: No; Mild: Slightly uncomfortable when pressure; Moderate: Discomfort upon movement; Severe: Discomfort at rest)
  - Redness at injection site in past 24 hours (Dia\_Redness; levels: No; Yes, <2.5 cm in diameter; Yes, 2.5-5 cm in diameter; Yes, 5.1-10 cm in diameter; Yes, >10 cm in diameter)

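### SAP 4.4.7 reports the graded on-site injection-site ratings only as a count of reactors, with no grade, item, injection number or listing, and leaves 8 on-site systemic items without a summary

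*SAP*

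**What the plan says.** SAP 4.4.7 consists of one sentence: "The number and percentage of participants with reaction at injection site will be summarized and presented by treatment group and overall".

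The ratings behind it are defined in SAP 2.2, under the heading for local tolerability at the injection site. Most are graded. A local example is "Redness at injection site (levels: No; Yes, <2.5 cm in diameter; Yes, 2.5-5 cm in diameter", which continues to more than 10 cm. The same heading also holds systemic items, such as "Diarrhoea (levels: No; Yes, 1-3 times; Yes, 4-6 times; Yes, >6 times" and "Physical discomfort (levels: No; Mild: Does not interfere with daily life". Only one item is a plain yes/no: "Other abnormalities at injection site (levels: No or Yes".

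Collection is tied to each dose. Protocol Table 1 marks the injection-site review on the three dosing visits and on the visits one week later. Note 1 places it before the injection, and note 3 adds: "Also performed 45 minutes (+/- 15 minutes) and approximately 6 hours after administration of study IP at each applicable visit". The Protocol synopsis (Study Design) says that participants "will have an onsite visit 1 week after each dose of study IP, to review for any injection site reactions and/or adverse events".

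Two other SAP sections deal with severity. Section 4.4.8 lists the participant-reported eDiary data and tabulates symptom presence and severity by treatment group. Section 4.4.1 tabulates TEAEs by intensity.

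**The concern.** Tolerability is a primary objective, and it was one basis for choosing the Part B doses: "dose(s) levels were selected based on interim analysis of safety, tolerability and immunogenicity data". The site collects graded ratings at fixed times around each injection, but the SAP uses none of that detail. A percentage of reactors does not separate mild redness from a severe reaction, does not say which item was involved, and does not say which injection came before it.

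The last gap matters because three regimens change dose part-way. Cohorts 3 and 4 are dosed concurrently and differ only in the first injection, as do Cohorts 5 and 6. Cohorts 8 and 9 differ only at Weeks 5 and 13. Any tolerability difference within these pairs shows most clearly by injection, and no planned table is laid out that way.

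The mixed heading raises a second question: where the on-site ratings of diarrhoea, headache and the other systemic items will be reported.

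**Working it through.** The plan states no figure to reproduce here. The check is a count and a comparison of sections.

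**1. Items under the SAP 2.2 heading**
- Injection-site (6): hard knot, other abnormalities, painfulness, redness, swelling, tenderness.
- Systemic (8): diarrhoea, dizziness, fatigue, fever, headache, muscle pain, nausea/vomiting, physical discomfort.
- Total: 6 + 8 = 14. All but other abnormalities have 4 or 5 levels, so 13 of 14 are graded, including 5 of the 6 local items.

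**2. Match with the eDiary list in SAP 2.2**
- Graded local items: 5 of 5, with the same levels.
- Systemic items: 7 of 8. Physical discomfort has no counterpart, and nausea/vomiting is matched by vomiting only. The eDiary also has an ungraded item for other symptoms.

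**3. Timing**
- Injections fall on Days 1, 29 and 85. On-site review is before the dose, at about 45 minutes, at about 6 hours, and on Days 8, 36 and 92. That is 3 post-dose reviews per injection, or 3 × 3 = 9 in all.
- Protocol Table 1, note 14 has participants record at home for 6 days from the day after dosing: nominally Days 2–7, 30–35 and 86–91. I take this to be the eDiary. It ends the day before each one-week visit.

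**4. Planned outputs**

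| Output | On-site (4.4.7) | eDiary (4.4.8) | TEAEs (4.4.1) |
|---|---|---|---|
| Listing | not named | yes | yes |
| Severity table | not named | yes | yes |
| Breakdown by item or term | not named | by symptom | by SOC and PT |
| Table by injection | not named | not named | not named |
| The 8 systemic items | not named | 7 of 8 | only if recorded as AEs |

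The interim review list in SAP 1.11.2 names no injection-site or eDiary output. In the available text, 4.4.7 is therefore the only section that says how the on-site ratings are summarised.

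**5. Participants whose dose changes** (Protocol synopsis; SAP 1.10)
- Planned active: 7 cohorts × 6 + 2 cohorts × 7 = 42 + 14 = 56.
- Dose changes in Cohort 3 (40 then 300 µg), Cohort 5 (40 then 1000 µg) and Cohort 8 (300 then 100 µg): 6 + 6 + 7 = 19.
- 19/56 = 33.9%.

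**6. A hypothetical case.** Suppose all 6 vaccinees react in each of two cohorts, mildly in one and severely in the other. The 4.4.7 table shows 6/6 (100%) for both.

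**The case against.** The strongest answer is that severity is still reported. A reader might infer from 4.4.7 that severity by dose regimen is lost. The documents do not support that: 4.4.8 tabulates it by treatment group for all 5 graded local items and 7 of the 8 systemic ones, and 4.4.1 does so for TEAEs. The two cohorts in the hypothetical case would be told apart if participants recorded their reactions. The eDiary items also ask about the past 24 hours, so the first entry looks back over most of the injection day. What remains is that the eDiary is self-reported, stops before the one-week visit and does not replace the timed on-site ratings. The available text does not say whether every graded reaction is also recorded as an AE.

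Other stronger readings also go too far:
- **One yes/no over the whole study.** The SAP is silent on how the three injections are combined. In 4.4.1, overall refers to treatment groups, and it probably does here too.
- **Investigator-rated.** No rater is named. This is inferred from the contrast with the participant-reported list.
- **Systemic items counted as local reactions.** On its plain wording 4.4.7 counts injection-site reactions only, so these items are unsummarised rather than miscounted.
- **The percentage will reach its ceiling.** No reaction rate is given. If the three injections were pooled and independent, with per-dose probability p, the any-reaction rate would be 1 − (1 − p)³: 65.7%, 87.5% and 97.3% for assumed p of 0.3, 0.5 and 0.7. The chance that all 6 vaccinees react would be that rate to the sixth power: 8%, 45% and 85%. Saturation is possible, but the documents do not establish it.

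It is also fair to say that comparison by assigned regimen is what the plan intends, that the AE listing carries occasion, dosing date and start time, and that tables by item, grade and injection will be sparse with 6 or 7 active participants per cohort. The listing helps only for reactions recorded as AEs. Sparse cells argue for a compact worst-grade layout, not for omitting the grade.

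**Conclusion.** The point holds for the on-site ratings and for the link to an injection. SAP 4.4.7 leaves the grades of 13 of 14 items unused and names no listing, although the neighbouring 4.4.8 provides both a listing and a severity table for the equivalent diary items. The 8 on-site systemic items have no planned summary, and physical discomfort has no graded diary counterpart either.

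The gap by injection affects 4.4.7 and 4.4.8 alike. For 19 of 56 planned active participants (34%), the summary tables cannot tie a reaction to the dose given. This is a limit of the tables: dates in the eDiary and AE listings may still allow a case-by-case reading.

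The conclusion rests on reading silence in 4.4.7 as no planned output, and on taking the eDiary to be the home record in note 14. It does not depend on any assumed reaction rate.

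**What to change.** Amend SAP 4.4.7 to:
- list the on-site ratings by participant, injection and time point;
- tabulate, for each item, each participant's worst post-dose grade by injection (1, 2, 3) and regimen, with pooled placebo as in SAP 3.6;
- count only the 6 injection-site items as local reactions, and report the 8 systemic items in a separate table of the same form.

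Apply the same split by injection to the eDiary tables in 4.4.8, and relabel the mixed heading in SAP 2.2 to match.

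The cost is SAP wording and extra frequency tables from data already collected, with no new assessments or participants. The drawback is more tables with small cell counts, which should be read descriptively. If the SAP can no longer be amended, the tables can be added and documented in the study report under SAP 4.6.
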